### 13.1 Study Blinding and Unblinding (Group 1)

Study subjects and site staff (except for the NIH pharmacists) will be blinded to the subject treatment arm assignments (e.g., active treatment or control). Any discussion about the study product assignment between the pharmacy staff and any other protocol staff is prohibited. The Data and Safety Monitoring Board (DSMB) members also are unblinded to the treatment assignment for the review of trial safety.

When a subject leaves the trial prior to study completion, the subject will be told he or she must wait until the all the subjects are unblinded to learn about his or her treatment assignment.

Emergency unblinding decisions will be made by the PI. If time permits, the sponsor medical monitor will be consulted before emergency unblinding occurs.

#### 14 STATISTICAL CONSIDERATIONS

The primary safety outcome is the occurrence of grade 3 or higher AEs. An exact 95% confidence interval for the probability of AEs will be computed using the Clopper-Pearson method. The primary efficacy outcome is rebound of plasma viremia requiring a restart of ART. An exact 95% confidence interval will be computed for the rebound probability using the Clopper-Pearson method. Changes from baseline in continuous measurements will be analyzed using paired t-tests or, if data are skewed, the Wilcoxon signed rank statistic.

In terms of safety, a sample size of 30 subjects provides a 95.8% chance of observing an AE of probability 10% or greater. Table 1shows the chance of observing at least one AE of given probability.

Table 1. Chance of AE of Given Probability

		Р	robability			
Row 1	0.025	0.050	0.075	0.100	0.125	0.150
Row 2	0.532	0.785	0.904	0.958	0.982	0.992

The second row is the probability of observing at least one AE of probability given in the first row for the 30 subjects receiving 3BNC117 plus 10-1074.

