# 3.2 Study Endpoints

# 3.2.1 Primary Endpoint

The rate of occurrence of grade 3 or higher AEs, including SAEs, that, per standard criteria (see safety Section 12.3.1) are probably or definitely related to the test article.

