# 6.4 Follow-up Phase

Group 1: Subjects in Group 1 will enter the follow-up Phase when they meet criteria to re-start ART and will be seen 4, 12, and 24 weeks after restarting ART to ensure viral suppression has been achieved.

Group 2: Subjects in Group 2 will enter the follow-up Phase after their final 3BNC117/10-1074 infusion and will be seen 4, 12, and 24 weeks after the last antibody infusion.

At these visits, subjects in both groups will undergo the following procedures:

- Interval medical history and a targeted physical examination, including weight, vital signs, and a symptom-directed evaluation based on symptoms or complaints reported by each subject
- Assessment of any new or unresolved AEs or intercurrent illnesses
- Blood collection for:
  - CBC with differential
  - Chemistry panels, to include: ALT, AST, ALP, creatinine, total and direct bilirubin, and serum albumin levels
  - Flow cytometry panel (includes CD4+ T cell count)
  - Plasma HIV viral level
  - HIV genotype (Group 1; if viral level is >1,000 copies/ml)
  - Storage of serum, plasma and PBMCs

Subjects in Group 2 will also have optional blood draw visits for CD4 counts, plasma viral level, and storage at 2, 6, 8, 10, 16, and 20 weeks after the last antibody infusion which may be drawn at NIH or offsite.

For participants who are unable to return to the NIH CC during the COVID-19 pandemic due to travel restrictions, blood samples may be collected at their local clinics or Quest Diagnostics and sent to the NIH CC for testing which will include; CBC with differential, plasma HIV viral level, and flow cytometry. Chemistry panels may be run at Quest Diagnostics laboratories and the

results sent to the NIH Study team. A study provider (Nurse Practitioner, Physician's Assistant, or Physician) will contact participants by phone and obtain an interval medical history.

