# 12.3 Investigator Assessment of Adverse Events

If a diagnosis is clinically evident (or subsequently determined), the diagnosis rather than the individual signs and symptoms or lab abnormalities will be recorded as the AE.

All AEs occurring from the time when the first infusion is administered through the specified study follow-up period will be documented, recorded, and reported. The PI will evaluate all AEs with respect to **Seriousness** (criteria listed above), **Severity** (intensity or grade), and **Causality** (relationship to study agent and relationship to research) according to the following guidelines.

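### The primary safety analysis is a single per-subject probability over a follow-up that lengthens when the antibodies work, with an endpoint worded differently in two places and no adverse-event comparison with the randomised placebo arm

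*Combined protocol and SAP*

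**What the plan says.** Section 3.2.1 defines the primary endpoint as "The rate of occurrence of grade 3 or higher AEs, including SAEs" that "are probably or definitely related to the test article". Section 14 restates it without the relatedness condition: "The primary safety outcome is the occurrence of grade 3 or higher AEs". The planned analysis is a one-sample interval: "An exact 95% confidence interval for the probability of AEs will be computed using the Clopper-Pearson method". Section 14 does not say for which subjects the interval is computed. Table 1, which supports the safety sample size, is "for the 30 subjects receiving 3BNC117 plus 10-1074", that is, 15 from Group 1 and 15 from Group 2.

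Neither section gives a period. Section 12.3 sets the collection rule: "All AEs occurring from the time when the first infusion is administered through the specified study follow-up period will be documented". Under Section 6.4, Group 1 subjects "will be seen 4, 12, and 24 weeks after restarting ART to ensure viral suppression has been achieved", and Group 2 subjects "will be seen 4, 12, and 24 weeks after the last antibody infusion". Section 3.1 lets the Group 1 treatment interruption run to week 64, and Section 6.3 lets it run longer while viral load stays below 40 copies/mL. Infusions stop once Group 1 restart criteria or Group 2 removal criteria are met (Section 3.1).

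The only between-arm difference planned is the efficacy endpoint in Section 3.2.2.

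**The concern.** A binomial proportion has a clear meaning when every subject is observed for the same period. Here the period is set partly by efficacy: a subject who stays suppressed off ART is observed longer and, up to week 24, receives more infusions. The reported probability then depends on how well the antibodies worked as well as on how safe they are, and it cannot readily be compared with another study.

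Group 1 also contains a blinded, randomised saline arm that stops ART at the same time and follows the same visit and restart rules. It is the only randomised reference for events due to the interruption, the procedures or background illness. The stated primary safety analysis does not use it, and half of the subjects behind Table 1 are open-label and uncontrolled.

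How much this matters depends on which endpoint definition governs, and the two sections disagree on that.

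**Working it through.** **The plan's own figure.** Table 1 is 1 − (1 − p)^30. For p = 0.025, 0.050, 0.075, 0.100, 0.125 and 0.150 this gives 0.532, 0.785, 0.904, 0.958, 0.982 and 0.992. All six entries are reproduced. At p = 0.10, n = 15 would give 0.794 and n = 45 would give 0.991, so the table covers the antibody recipients only.

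**Length of follow-up (Sections 3.1, 5.1, 6.4).**
- Group 1: restart week + 24. Restart at week 6 gives 30 weeks, at week 28 gives 52, and at week 64 gives 88. The ratio 88/30 is about 2.9.
- Group 2 completer: 24 + 24 = 48 weeks, and less after early removal.

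**Expected imbalance under the plan's restart assumptions.** Section 14 assumes restart probabilities of 0.80 on placebo and, in the first column of Table 2, 0.20 on antibody. I apply both at week 28, the efficacy cut-off. *Assumption:* restart time T has a constant hazard λ after a lag L of 0, 4 or 6 weeks, with λ = −ln(1 − q)/(28 − L) for restart probability q. Follow-up is F = min(T, 64) + 24, with mean

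24 + L + [1 − exp(−λ(64 − L))]/λ.

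For L = 0:
- q = 0.80: λ = 0.0575 per week; mean F = 24 + 17.0 = 41 weeks.
- q = 0.20: λ = 0.0080 per week; mean F = 24 + 50.1 = 74 weeks.

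Across the three lags, mean follow-up is 41–43 weeks against 74 weeks. Mean infusions received are 4.8–5.6 against 7.4–7.5.

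**Effect on an all-cause proportion.** *Assumption:* the same constant AE hazard h in both arms, so no drug effect. The values of h are illustrative. The per-subject probability is 1 − E[exp(−hF)], and over a fixed 28 weeks it is 1 − exp(−28h/52).

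| h per person-year | q = 0.80, open window | q = 0.20, open window | Fixed 28 weeks, either arm |
|---|---|---|---|
| 0.1 | 7.5–8.0% | 13.2% | 5.2% |
| 0.2 | 14.4–15.3% | 24.5% | 10.2% |

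The single-arm estimate moves too. At h = 0.1, changing the antibody-arm restart probability from 0.50 to 0.10 moves it from about 10% to about 14%.

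**Effect on a related-event proportion.** A probably or definitely related event needs a reasonable temporal relationship (Section 12.3.1). The last infusion is at week 24, and the stated half-lives are 18 and 24 days. Background events at weeks 40 to 88 would rarely qualify, so the table above does not describe the Section 3.2.1 endpoint. What remains is the unequal number of infusions.

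**Precision.** Clopper-Pearson upper limits are 11.6% for 0/30, 17.2% for 1/30 and 21.8% for 0/15. For a 15 versus 15 difference, Newcombe 95% intervals are −20.4 to +20.4 points at 0/15 versus 0/15, and −9.2 to +37.9 points at 2/15 versus 0/15. Fisher's exact test (two-sided 0.05) has 16% power for 0% versus 20%.

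**The case against.** The strongest reply is that Section 3.2.1 counts only probably or definitely related events, graded in Group 1 by blinded staff. Such events were rare in the earlier studies: no related grade 3 or 4 AEs with 3BNC117 (Section 1.1.3.1), no related grade 3 AEs with 10-1074 (Section 1.1.3.2), and one severe related AE in Appendix A. With zero or one event in 30, the window hardly changes the interval. This stands for Section 3.2.1, but it does not rescue Section 14, which omits relatedness.

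A second reply is that an exact one-sample interval is normal in an exploratory Phase 1 trial, that the placebo arm was included for efficacy (Section 1.2), and that 15 versus 15 says little. That rules out a powered test. It does not rule out an estimate from data already collected.

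Third, the plan does not exclude a placebo interval, AE frequency tables go to the sponsor (Section 12.4.1), and the DSMB sees unblinded safety data (Section 13.1). This is correct, but none of it is a stated comparison.

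Fourth, a common window does not isolate the antibody effect. Placebo subjects who restart are back on ART and no longer infused, so dose count and time off ART differ by arm even within 28 weeks. A week-28 limit also falls only four weeks after the last infusion and would omit late events. Both points stand and shape the fix.

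**Conclusion.** The point holds as an improvement to Section 14. The summary has no fixed period, its follow-up and dose count depend on efficacy, no randomised AE comparison is stated, and the endpoint wording differs from Section 3.2.1. For all-cause grade 3 or higher AEs the distortion could be about 5 points at a hazard of 0.1 per person-year and 9 to 10 points at 0.2. These sizes rest on assumed, constant, equal AE hazards and a constant restart hazard. For related events it is likely small.

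A reader might infer more than the documents support:
- *That the planned safety result is biased against the antibodies by some 10 points.* That figure needs all-cause counting, an assumed hazard and even ascertainment. The Group 1 extended-interruption flow sheet in Appendix B has no AE-assessment row, unlike the infusion and follow-up sheets, so late events may be under-detected and even the direction is uncertain.
- *That Table 1 is wrong.* Its arithmetic is right, but its p is tied to no period.
- *That rate in Section 3.2.1 contradicts probability in Section 14.* A rate of occurrence is often used to mean a proportion.

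**What to change.** In Section 14, before unblinding:

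1. Reconcile the primary safety outcome with Section 3.2.1 on relatedness.
2. Pre-specify one window common to all subjects, counted by AE onset date, and report the proportion with an event in it, with the Clopper-Pearson interval for the 30 antibody recipients. Beside it, report full-follow-up events per person-year with an exact Poisson interval, so that late events are not lost. If week 28 is chosen, state how Group 2 subjects whose last infusion is at week 0 or 2 are handled, since their follow-up ends at week 24 or 26.
3. Add the Group 1 antibody-minus-placebo difference in that window with an exact 95% interval, for related and for all-cause grade 3 or higher AEs. Label it as estimation, not a powered test, and note that dose count and time off ART still differ by arm.
4. Show Group 2 separately as well as pooled.

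The extended-interruption flow sheet should also be reconciled with the AE collection rule in Section 12.3.

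The cost is some wording and one extra table, with no new subjects. The interval for the difference will be wide, about ±20 points if neither arm has an event.

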## 1.2 Rationale

The objectives of this study are to evaluate the safety and virologic efficacy of multiple doses of 3BNC117 and 10-1074 in two groups of HIV-infected individuals. Group 1 will enroll ART-treated subjects who began therapy during primary HIV infection. Individuals who began ART during primary HIV infection exhibit less viral diversity within their reservoir of persistently infected CD4+ T cells and are thus, less likely to harbor HIV quasispecies resistant to neutralization by 3BNC117 or 10-1074. A second rationale for limiting Group 1 to individuals who began ART during primary infection is to investigate whether treatment with 3BNC117 plus 10-1074 results in long-term suppression of plasma viremia in the absence of both ART and mAb treatment, as was observed in the SHIV primate study described in Section 1.1.2. Subjects in Group 1 will be randomized into two arms; mAb treatment (3BNC117 plus 10-1074) or placebo. The use of a placebo arm in Group 1 is necessary as a significant proportion of individuals who began ART during primary infection will maintain viral suppression, in the absence of any intervention, for at least 6 months following discontinuation of ART.

Group 2 will enroll individuals with HIV viremia who are not receiving ART. Inclusion of this group will allow us to investigate the antiviral activity of the study mAbs in subjects with stable viremia in the absence of recent ART. Furthermore, the feasibility of achieving sustained

virologic remission and induction of long-lasting anti-HIV immunity in individuals with relatively low levels of plasma viremia who are not taking ART will be addressed in this group.

The efficacy of treatment with this bNAb combination will be determined by its effect on viral rebound following discontinuation of ART in Group 1 and on plasma viremia in Group 2.

The rationale for using the proposed dose of 3BNC117 and 10-1074 is based on the safety and pharmacokinetic data generated from Phase I human studies.

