# 2.3 Exploratory Objectives

- To investigate whether 3BNC117 and 10-1074 -mediated suppression of HIV replication in the absence of ART allows the development of anti-HIV immunity (i.e., CTL response).
- To investigate the capacity of 3BNC117 and 10-1074 to neutralize replication-competent HIV prior to and following administration of the study drugs.
- To examine and characterize ex vivo 3BNC117 and 10-1074-escape mutants that might develop during the study.

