#### 3 STUDY DESIGN

# 3.1 Description of the Study Design

The proposed trial will be a triple-arm study to examine the effect of 3BNC117 combined with 10-1074 in two groups of HIV-infected individuals. In Group 1, 30 individuals who began ART during primary HIV-1 infection will be randomized 1:1 to treatment with 3BNC117 plus 10-1074 or normal saline placebo. Study staff and participants will be blinded to Group 1 treatment assignments. Efficacy will be measured in this group by comparing the number of subjects in the treatment and placebo arm who meet criteria to restart ART during the ATI-treatment phase of the study (weeks 0-28).

For study Group 2, up to 15 viremic individuals not taking ART will receive 3BNC117 combined with 10-1074. Efficacy will be measured in this group by the proportion of subjects in whom mAb treatment is able to suppress plasma viremia during the treatment phase (weeks 0-28). Study subjects will receive infusions of 3BNC117 (30mg/kg) and 10-1074 (30mg/kg) or placebo (Group 1) at study days 0, Week 2, Week 4, and every four weeks thereafter for up to 24 weeks (Figure 1).

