# 3.2.2 Secondary Endpoints

Difference between the treatment and placebo arms in the number of subjects in study Group 1 who experience rebound of plasma viremia and meet criteria to restart ART prior to study week 28.

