#### 6.3 ATI/Treatment Phase

Subjects will be administered 3BNC117 and 10-1074/ placebo on study day 0. All subjects in Group 1 will discontinue their ART regimen after study day 3. Subsequent infusions of 3BNC117 and 10-1074/placebo will occur at study Week 2, 4, and every four weeks thereafter until study Week 24 for a total of 8 doses (see Figure 1).

Storage of plasma, serum, and cells may be done at study day 0, Week 2, 4 and every 2 weeks thereafter for the duration of the ATI-Treatment phase. Flow cytometry (including CD4 count) and Plasma HIV viral RNA levels will be done every 2 weeks for the duration of the ATI-Treatment Phase. HIV genotype will be obtained on all samples with HIV viral levels >1,000 copies/ml. For select subjects residing outside the local (Bethesda, MD) area, blood samples for blood draw only visits, may be collected at their local clinics or Quest Diagnostics and sent to the NIH Clinical Center for testing. Samples collected at clinics or at Quest may be labeled with a coded identifier, gender, and date of birth, as required by the local facility.

At infusion visits, the following will be done in addition to the flow cytometry panel and plasma HIV viral level:

- Interval medical history and a targeted physical examination, including weight, vital signs, and a symptom-directed evaluation based on symptoms or complaints reported by each subject
- Assessment of concomitant medications
- Assessment of any new or unresolved AEs/intercurrent illnesses
- Blood collection:
  - CBC with differential
  - Chemistry panels, to include: ALT, AST, ALP, creatinine, total and direct bilirubin, and serum albumin levels
- Serum or urine pregnancy test for women of child-bearing potential (results must be reviewed prior to infusion)
- Optional leukapheresis for research studies will be done at Week 0, 16 and within +/14 days of the week 24 infusion
- HIV transmission risk behavior assessment and counseling

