# 7.2 Laboratory Evaluations

# 7.2.1 Clinical and Research Laboratory Evaluations and Specimen Collection

- HIV viral RNA levels
- HIV genotype (if viral level is >1,000 copies/ml)
- Flow cytometry with CD4+ T cell count
- Routine serologic, hematologic, and clinical chemistry evaluations as described in Section 6

Leukapheresis: Will be performed for research studies including, but not limited to, measurements of the frequency of CD4+ T cells carrying HIV proviral DNA, cell-associated RNA, and replication-competent virus by quantitative co-culture assays. These studies will address the exploratory endpoints. If leukapheresis cannot be performed for technical reasons (e.g., poor venous access), 80 ml of blood will be drawn instead.

Other research evaluations measuring the effect of 3BNC117 and 10-1074 on the HIV pathogenesis may include:

- Frequency of CD4+ T cells carrying HIV proviral DNA and cell-associated HIV RNA
- Levels of cell-associated infectious virus
- Sequencing of viral DNA and RNA
- Neutralization assays using replication-competent HIV against bNAbs
- Frequency of HIV-specific CD4+ and CD8+ T cells
- Markers of T-cell activation, immune exhaustion, and inflammation

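### Section 14 plans only paired before-after tests for continuous measures, which in Group 1 cannot separate an antibody effect from the effect of stopping ART

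*Combined protocol and SAP*

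**What the plan says.** Section 14 covers continuous outcomes in one sentence: "Changes from baseline in continuous measurements will be analyzed using paired t-tests or, if data are skewed, the Wilcoxon signed rank statistic". It does not distinguish Group 1 from Group 2, or antibody from placebo. Neither it nor any other section gives a between-arm test, a baseline-adjusted model or a longitudinal model for CD4 count, viral load or the research assays.

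Group 1 is a randomised comparison (Section 3.1): "30 individuals who began ART during primary HIV-1 infection will be randomized 1:1 to treatment with 3BNC117 plus 10-1074 or normal saline placebo". Section 1.2 justifies the control: "The use of a placebo arm in Group 1 is necessary", because some early-treated people stay suppressed off ART with no intervention. Under Section 6.3, "All subjects in Group 1 will discontinue their ART regimen after study day 3".

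Section 7.2.1 introduces the list of proviral DNA, cell-associated RNA, T-cell frequency and activation assays with "Other research evaluations measuring the effect of 3BNC117 and 10-1074 on the HIV pathogenesis may include". Section 2.3 asks whether antibody-mediated suppression without ART "allows the development of anti-HIV immunity (i.e., CTL response)".

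The binary efficacy endpoint is treated differently. Section 3.2.2 defines it as "Difference between the treatment and placebo arms in the number of subjects in study Group 1 who experience rebound of plasma viremia" and meet the restart criteria, and Table 2 in Section 14 gives power for that arm comparison.

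**The concern.** A paired test asks whether a measure changed after baseline. In Group 1 the baseline is taken on ART, and ART ends days later in both arms. Every later change therefore combines interruption, any viral return and any antibody effect. The test can mislead in both directions. Interruption alone can produce a significant change in the antibody arm. Conversely, if the antibodies prevented a change that interruption would otherwise cause, the antibody arm would show no change and the benefit would be visible only against placebo.

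The questions in Sections 2.3 and 7.2.1 concern what the antibodies do. The randomised placebo arm, measured on the same schedule (Appendix B), is what can answer them, and the stated method for these measures makes no use of it.

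Testing each arm separately and comparing the p-values would not repair this. Significant in one arm and not in the other is not a test of the difference between arms.

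**Working it through.** **The plan's own figures.** Enumerating all outcomes for 15 versus 15 with a two-sided Fisher exact test at 0.05 and a placebo restart probability of 0.80 gives power 0.872, 0.840, 0.804, 0.765, 0.724 and 0.680 for antibody-arm probabilities 0.20 to 0.30. All six match Table 2. A one-sided Fisher test (0.939 at 0.20) and an uncorrected z-test (0.941) do not. So the restart endpoint was sized as a two-sided between-arm comparison, although Section 14 does not name the test. There is no corresponding figure for continuous measures.

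**Inputs.**
- n = 15 per arm (Section 3.1: 30 randomised 1:1).
- Two-sided alpha 0.05. This is assumed, because Section 14 states no alpha; it agrees with the 95% intervals and with Table 2.
- d = shift caused by stopping ART, in SDs of the change score. This is assumed, because the documents give neither an SD nor an expected change. It is taken as equal in both arms, with no antibody effect on the marker.

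**Paired t-test in the antibody arm.** The statistic is non-central t with n − 1 = 14 degrees of freedom and non-centrality d√15 = 3.873d. The rejection probability is q = P(|T| > t(0.975, 14)).

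| d | Non-centrality | q, antibody arm (n = 15) | Rejection, both arms pooled (n = 30) |
|---|---|---|---|
| 0.25 | 0.968 | 0.147 | 0.263 |
| 0.50 | 1.936 | 0.438 | 0.754 |
| 0.75 | 2.905 | 0.771 | 0.978 |
| 1.00 | 3.873 | 0.949 | about 1.00 |

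The last column covers a reading of Section 14 in which the Group 1 arms are pooled; it uses 29 degrees of freedom and non-centrality d√30.

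**Between-arm t-test on change.** A shift common to both arms cancels. The non-centrality is zero and the rejection probability is 0.05 for every d.

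**Separate paired tests in each arm.** The arms are independent, so the chance that the antibody arm is significant and placebo is not equals q(1 − q). At 0.5 SD this is 0.438 × 0.562 = 0.246. At 0.25 and 0.75 SD it is about 0.13 and 0.18.

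**Power of the alternative.** For a true arm difference δ in SD units, the between-arm test has 28 degrees of freedom and non-centrality δ√(15/2) = 2.739δ. Power is 0.262 at δ = 0.5, 0.509 at 0.75, 0.753 at 1.0 and 0.80 at about 1.06.

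**Subjects still off ART late in the phase, under Table 2's assumptions.** Placebo restarts: 0.80 × 15 = 12, leaving 3. Antibody-arm restarts at probability 0.20: 0.20 × 15 = 3, leaving 12.

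**The case against.** The strongest reply is that little in the plan depends on this sentence. The primary, secondary and exploratory endpoints in Section 3.2 are all counts or rates, and this is an exploratory Phase 1 study. Paired tests also suit part of what the sentence covers: Group 2 has one arm and no ART stop, and Section 1.2 assigns to Group 2 the question of lasting immunity in people with low viremia off ART. All of this stands, and it limits the point to exploratory and supportive measures. It does not make the paired test informative about the antibodies in Group 1; Section 2.3 does not confine the immunity objective to Group 2.

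A reader might infer three stronger things that the documents do not support.
- That the placebo arm goes unused. It is used for ART restart (Sections 3.1 and 3.2.2, Table 2).
- That the plan will credit paired changes to the antibodies. No section says so. Section 7.2.1 describes the assays as measuring antibody effects, but it is a list of evaluations that may be done.
- That the immunity objective will be declared met or not met on a paired p-value. No section sets such a rule, and none proposes comparing significance across arms.

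The size is also open to challenge. The shifts are assumed. At 0.5 SD the two arms' paired tests disagree in 2 × 0.246 = 49% of trials, but only half of those, about 25%, point falsely towards the antibodies. An equal shift in both arms is a no-effect scenario, whereas the plan expects restart in 80% versus 20–30%. For apheresis-based assays n = 15 is a maximum, since leukapheresis is optional (Sections 6.2 and 6.3).

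Finally, a between-arm test is not free of trouble. Subjects who meet restart criteria leave the infusion schedule (Section 3.1) and are then seen 4, 12 and 24 weeks after restarting (Section 6.4), with apheresis at follow-up week 24 (Appendix B). Late values would mix antibody effect with ART status. That objection is correct and shapes the fix. It does not rescue the paired test, which has the same missing and post-restart values and no control.

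**Conclusion.** The point holds for continuous measures in Group 1. The only stated test cannot distinguish the antibodies from ART interruption, and data that can are already being collected under blinding. It is a moderate matter: no named endpoint changes, and Tables 1 and 2 stand.

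The 15%, 44% and 77% figures illustrate how quickly the problem grows with the assumed shift; they are not forecasts. They rest on 15 evaluable subjects per arm, two-sided 0.05, roughly normal change scores and an equal interruption effect in both arms. The qualitative conclusion does not depend on the shift chosen, provided that stopping ART moves the marker at all.

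**What to change.** In Section 14, for Group 1:
- Make the main analysis of each continuous measure a between-arm comparison: ANCOVA of the follow-up value on arm and baseline, or a rank-sum test on change if skewed, with a 95% confidence interval for the arm difference. State alpha and sidedness.
- Name one time point within the ATI/treatment phase for each measure. Week 16 is an existing apheresis visit; the documents do not say how many subjects will have restarted by then.
- State how values that are missing or measured after ART restart are handled. One option is the last value before restart, with a sensitivity analysis using all values. Because placebo subjects are expected to restart more often, their last values may come sooner after the ART stop, so the sensitivity analysis is needed.
- Keep paired tests as within-arm description.

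For Group 2, keep the paired tests and label them uncontrolled.

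The cost is a short paragraph written before unblinding, with no new subjects, visits or assays. The downside is precision: 80% power only for a difference of about 1.06 SD on change scores (ANCOVA may do somewhat better where baseline predicts follow-up). Unequal restart will still limit what late time points can show.
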